7. SUBJECT ENROLLMENT AND WITHDRAWAL

7.1 SUBJECT POPULATION

A total of 170 hips will be enrolled into the study at 4 study sites in China.

Subjects may be enrolled and randomized in the study with one hip implanted with either the OR3O™ Dual Mobility System in combination with R3™ Acetabular Shells and a Smith & Nephew Oxinium femoral head or the single-bearing design Total Hip System comprised of R3™ Acetabular Shell with XLPE liner and a Smith & Nephew Oxinium femoral head. Therefore, enrollment refers to the number of subjects.

7.2 INCLUSION CRITERIA

Subjects will be considered qualified for enrollment if they meet the following criteria:

CONFIDENTIAL AND PROPRIETARY

This document contains information that is confidential and proprietary to Smith & Nephew PLC and Smith & Nephew, Inc. and is intended for use only by Smith & Nephew and its manufacturer. It shall not be reproduced or copied in whole or in part, nor shall the contents be disclosed by any means without prior written permission from Smith & Nephew, nor shall anyone make any use of it that is contrary to the expressed or implied wishes of Smith & Nephew.

Clinical Protocol	Study Number: OR3O.2019.10 (China)
Prospective, Multi-center, Randomized, Controlled Study to Evaluate the Safety and Efficacy of the OR3O™ Dual Mobility System versus conventional single bearing design Total Hip System in Primary Total Hip Arthroplasty (THA) Procedures	Version: 1.0, 18Aug2020
	Page: 30 of 90

1. Subject is a suitable candidate for implanting the OR3O™ Dual Mobility System in primary total hip replacement in the Investigator’s judgement.
2. Subject is skeletally mature in the Investigator’s judgement.
3. Subject is 18 – 80 years old (inclusive).
4. Subject is receiving total hip replacement for the first time on the affected hip.
5. Subject has any of the following conditions:
 - Advanced degeneration of the hip joint as a result of degenerative, post-traumatic, or rheumatoid arthritis(RA);
 - Fracture or avascular necrosis of the femoral head;
 - All forms of osteoarthritis(OA);
 - Patients with hips at risk of dislocation;
 - Femoral neck fracture or proximal hip joint fracture.
6. Subject provides written informed consent for study participation using an Ethical Committee (EC) approved consent form before any study procedures are performed, including pre-operative data review and/or collection of data on Case Report Forms.
7. Subject is willing and able to participate in required follow-up visits and is able to complete study activities.
8. Subjects with preoperative HHS \leq 79 (fair or worse category).

7.3 EXCLUSION CRITERIA

Any one (1) of the following criteria will disqualify a potential subject from participation in the study:

CONFIDENTIAL AND PROPRIETARY

This document contains information that is confidential and proprietary to Smith & Nephew PLC and Smith & Nephew, Inc. and is intended for use only by Smith & Nephew and its manufacturer. It shall not be reproduced or copied in whole or in part, nor shall the contents be disclosed by any means without prior written permission from Smith & Nephew, nor shall anyone make any use of it that is contrary to the expressed or implied wishes of Smith & Nephew.

Clinical Protocol	Study Number: OR3O.2019.10 (China)
Prospective, Multi-center, Randomized, Controlled Study to Evaluate the Safety and Efficacy of the OR3O™ Dual Mobility System versus conventional single bearing design Total Hip System in Primary Total Hip Arthroplasty (THA) Procedures	Version: 1.0, 18Aug2020
	Page: 31 of 90

1. Subject has conditions that would eliminate or tend to eliminate adequate implant support or prevent the use of an appropriately-sized implant, e.g.:
 - blood supply limitations;
 - insufficient quantity or quality of bone support, e.g., osteoporosis, metabolic disorders which may impair bone formation, radioactive bone disease, tumor around hip joint, and osteomalacia;
 - infections or other conditions which may lead to increased bone resorption.
2. Subject has dysplasia of hip joint with CROWE Grade III, IV.
3. Subject has weak constitution or failing to endure the surgery due to other diseases of the body.
4. Subject has bodily disease(s) that may interfere with THA survival or outcome
5. Subject has life expectancy of less than 2 years.
6. Subject has mental or neurological conditions which impair the subject’s ability or willingness to restrict activities that may put the affected limb at risk.
7. Subject has physical conditions or activities which tend to place extreme loads on implants, e.g., Charcot joints, muscle deficiencies, multiple joint disabilities.
8. Subject has neuromuscular dysfunctions (paralysis, myolysis and abductor muscle weakness) which will cause unstable hip joint or abnormal gait after surgery.
9. Subject has a mental or neurological condition that would pre-empt their ability or willingness to participate in the study including mental illness, mental retardation, drug or alcohol abuse.
10. Subject has an active infection – systemic or at the site of intended surgery.
11. Subject has a Body Mass Index ≥ 40.0 kg/m²
12. Subject has a known allergy to any component of the devices used in the study.
13. Subject is pregnant or breast feeding.
14. Subject is entered in another investigational drug, biologic, or device study within 30 days of active study participation.

CONFIDENTIAL AND PROPRIETARY

This document contains information that is confidential and proprietary to Smith & Nephew PLC and Smith & Nephew, Inc. and is intended for use only by Smith & Nephew and its manufacturer. It shall not be reproduced or copied in whole or in part, nor shall the contents be disclosed by any means without prior written permission from Smith & Nephew, nor shall anyone make any use of it that is contrary to the expressed or implied wishes of Smith & Nephew.

Clinical Protocol	Study Number: OR3O.2019.10 (China)
Prospective, Multi-center, Randomized, Controlled Study to Evaluate the Safety and Efficacy of the OR3O™ Dual Mobility System versus conventional single bearing design Total Hip System in Primary Total Hip Arthroplasty (THA) Procedures	Version: 1.0, 18Aug2020
	Page: 32 of 90

- | | |
|-----|---|
| 15. | Subjects that are expected with poor compliance. |
| 16. | Subjects with complications of other diseases are limited to participate in the research, not able to comply with the follow-up or have impact on scientific integrity. |
| 17. | Subjects with preoperative HHS ≥ 80 (good to excellent category). |
| 18. | Subject has other diseases or conditions that investigator considers not appropriate to participate in the study. |

7.4 SCREENING

Investigators should consecutively screen all subjects undergo primary THA to determine whether they meet all inclusion and none of the exclusion criteria. Participating study sites are required to document all screened subjects considered for inclusion in this study on a Screening and Enrollment Log. If a subject is excluded from the study, the reasons for exclusion will be noted on the Screening and Enrollment Log.

7.5 INFORMED CONSENT

Investigators are responsible for obtaining and documenting the voluntary informed consent of the study subjects before conducting any study procedures or examinations, per International Conference on Harmonization (ICH) and Good Clinical Practice (GCP) guidelines.

Prior to beginning the study, in obtaining the informed consent, the purpose and nature of the study should be explained to the subject in their native language. The subject, will then **read, sign, and personally date** the EC approved informed consent document(s) (see below for difficulties with reading and writing). Additionally, the individual who obtains consent from the subject will sign and date the informed consent document. A copy of the signed informed consent document will be provided to the subject, and the original appropriately filed at the investigative site.

The informed consent process must be fully documented in the subject’s medical record.

If the subject is unable to read, the informed consent document and associated study information may be read aloud to the subject in the presence of an impartial witness. If possible, the subject shall sign and personally date the Informed Consent Form (ICF). Where this is not possible, due

CONFIDENTIAL AND PROPRIETARY

This document contains information that is confidential and proprietary to Smith & Nephew PLC and Smith & Nephew, Inc. and is intended for use only by Smith & Nephew and its manufacturer. It shall not be reproduced or copied in whole or in part, nor shall the contents be disclosed by any means without prior written permission from Smith & Nephew, nor shall anyone make any use of it that is contrary to the expressed or implied wishes of Smith & Nephew.

Clinical Protocol	Study Number: OR3O.2019.10 (China)
Prospective, Multi-center, Randomized, Controlled Study to Evaluate the Safety and Efficacy of the OR3O™ Dual Mobility System versus conventional single bearing design Total Hip System in Primary Total Hip Arthroplasty (THA) Procedures	Version: 1.0, 18Aug2020
	Page: 33 of 90

to difficulties in writing, the subject shall provide verbal consent to participate in the study. The witness shall then personally sign and date the informed consent form, attesting that the information was accurately explained and that the informed consent was freely given.

The informed consent form and any other written information provided to subjects shall be revised whenever important new information becomes available that may be relevant to the subject’s continued consent. All revised informed consent forms must have written and dated EC approval in advance of use.

7.6 ENROLLMENT

The site initiation shall be started only after the EC has approved and the clinical trial agreement has signed at each site. Subjects for whom the consent process has been completed and have been implanted with the study product are considered enrolled. Competitive enrollment continues until the completion of enrolled 170 subjects.

If the subject does not have the OR3O™ Dual Mobility System or controlled system implanted after signing an informed consent form, the subject will be considered to be a Screen Failure. Screen Failures will not count into the total number of enrolled subjects.

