7.8 WITHDRAWAL

7.8.1 Withdrawal from Treatment

Subjects may be withdrawn from having the study device implanted at a date close to surgery or during surgery for the following reasons:

- At the discretion of the Investigator due to:
 - A change in treatment being clinically warranted.
 - An adverse event.
 - Any other significant reason identified by the Investigator.

Subjects who provide informed consent but do not receive the study device for any reason will be considered a Screen Failure. Screen Failures will not count into the total number of enrolled subjects.

If at any point during the study, the study device needs to be revised for any reason the following will apply: Intraoperative data from the revision surgery will be collected including implant information used for revision THA. Subjects will terminate the study following revision surgery. Subjects shall be followed by the Investigator according to sites' standard of care in order to monitor the subject's health status and the outcome of the revision. Data collected following the revision surgery will be reported as follow-up data to the adverse event. Data will not be included as study data but presented separately as safety data. Data collected upon the point of revision will be included as study data.

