8.4.4 Safety Endpoints

Safety endpoints include the collection of the following events:

- All adverse events (AEs) occurring from the time of subject enrollment until study termination or study completion including intra-operative adverse events.
- Device Deficiencies.

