9.1.3 Operation Visit (Day 0) / Discharge

1. Collect information on any changes in subject general health and the use of concomitant medications. Update medical history as necessary.
2. Perform surgery and collect intraoperative data on source documents. This includes but is not limited to the following information:
 - Implant product – study arm or controlled arm
 - Implant data
 - Surgical data e.g. duration, surgical approach
 - AEs, Device Deficiencies

Any subject who signs an ICF but fails to be implanted with the study device for any reason is considered to be a Screen Failure.
3. At time of discharge, collect discharge data on source documents. This includes but is not limited to the following information:
 - Discharge Date
 - Mobility Status
 - Medication at discharge
 - AEs, Device Deficiencies
4. Based on standard of care at the study site, the investigator will decide whether the radiographic assessment will be performed prior to discharge or at the 6 weeks follow-up visit. Radiographic images are to be collected in anteroposterior (AP) and lateral view in supine position. Investigator to review the images and radiographic report, as well as record data in the subject's medical record.
5. Instruct the subject on follow-up procedures, including returning to the site for the follow-up visit in 6 weeks (42 days (- 7 days / +14 days) from the date of surgery).
6. Transcribe data to the eCRF.

CONFIDENTIAL AND PROPRIETARY

This document contains information that is confidential and proprietary to Smith & Nephew PLC and Smith & Nephew, Inc. and is intended for use only by Smith & Nephew and its manufacturer. It shall not be reproduced or copied in whole or in part, nor shall the contents be disclosed by any means without prior written permission from Smith & Nephew, nor shall anyone make any use of it that is contrary to the expressed or implied wishes of Smith & Nephew.

Clinical Protocol	Study Number: OR3O.2019.10 (China)
Prospective, Multi-center, Randomized, Controlled Study to Evaluate the Safety and Efficacy of the OR3O™ Dual Mobility System versus conventional single bearing design Total Hip System in Primary Total Hip Arthroplasty (THA) Procedures	Version: 1.0, 18Aug2020
	Page: 46 of 90

9.1.4 Follow-Up visit at 6 weeks post-surgery (42 - 7 days / + 14 days from the date of surgery)

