7.2 Analysis Populations

The following section details the analysis populations:

TMP-CD-30-01 Statistical Analysis Plan - Revision B; SOP-CD-30 Statistical Analysis

CONFIDENTIAL AND PROPRIETARY

This document contains information that is confidential and proprietary to Smith & Nephew PLC and Smith & Nephew, Inc. and is intended for use only by Smith+Nephew and its manufacturer. It shall not be reproduced or copied in whole or in part, nor shall the contents be disclosed by any means without prior written permission from Smith+Nephew, nor shall anyone make any use of it that is contrary to the expressed or implied wishes of Smith+Nephew.

Statistical Analysis Plan

A Prospective, Multi-center, Randomized, Controlled Study to Evaluate theVersion: 2.0,Safety and Efficacy of the OR3O[™] Dual Mobility System versus conventional29-Feb-2024single bearing design Total Hip System in Primary Total Hip Arthroplasty (THA)Page: 13 of 27ProceduresProcedures

Number: OR3O.2019.10 ST: 1100 Version: 2.0, 29-Feb-2024 Page: 13 of 27

Safety (SAF) Population: This is defined as all hips who have been implanted with the OR3O[™] Dual Mobility System or controlled system. The SAF population will be based on the device that is implanted into the hip and not the one the hip is randomized to (if different).

Full Analysis Set (FAS) Population: This is defined according to the basic principle of Intent-to-Treat (ITT) principle i.e., all implanted hips with at least one postoperative effectiveness, HRQoL or performance will be included in FAS Population.

Per-Protocol (PP) Population: The PP population is the subset of hips in the FAS population who do not have major protocol deviations and who satisfied all enrollment eligibility criteria. Criteria that can be regarded as major deviations will be formally classified on a case-by-case basis prior to the final study database lock.

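### Operated subjects who receive neither hip system are outside the safety population, so their intra-operative events reach no SAF-based safety summary

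*Protocol*

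**What the plan says.** **Enrolment.** Protocol 7.6: "Subjects for whom the consent process has been completed and have been implanted with the study product are considered enrolled". A subject who "does not have the OR3O™ Dual Mobility System or controlled system implanted after signing an informed consent form" is a Screen Failure and does not count towards the 170.

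**Randomisation.** Protocol 8.5.2 and SAP 6.2 allocate a randomisation number once consent is signed and eligibility is met. Implantation is not required.

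**Withdrawal around surgery.** Protocol 7.8.1: "Subjects may be withdrawn from having the study device implanted at a date close to surgery or during surgery for the following reasons". An adverse event is one of the reasons listed. It continues: "Subjects who provide informed consent but do not receive the study device for any reason will be considered a Screen Failure". The operation visit (Protocol 9.1.3) repeats the rule: "Any subject who signs an ICF but fails to be implanted with the study device for any reason is considered to be a Screen Failure".

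**AE window.** Protocol 8.4.4, repeated in SAP 5.7: "All adverse events (AEs) occurring from the time of subject enrollment until study termination or study completion including intra-operative adverse events".

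**Safety population.** SAP 7.2, following Protocol 10.2: "This is defined as all hips who have been implanted with the" test or control system. The SAP adds that the grouping follows the device implanted, not the device assigned. Protocol 10.5 and SAP 7.13 put all safety endpoints on this population.

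**The concern.** Safety is part of the primary objective (Protocol 5.1, SAP 5.1). Under these definitions an event during the operation can remove its own subject from the safety population: it stops the implantation, and without an implant there is no place in SAF. This exclusion happens after randomisation, and its cause may be related to the device. The test construct adds a liner with a locking taper and an insert with a snap-fit mechanism (Protocol 6.1.1), so the arms need not lose subjects at the same rate.

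SAP version 2.0 adds weight to this. Testing has been dropped, and SAP 7.10 and 7.11 summarise the primary and secondary endpoints on SAF as well. The opening of SAP section 7 still names the full analysis set for them, but SAP 7.2 limits that set to implanted hips too. A subject outside SAF is therefore outside nearly everything that will be reported.

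**Working it through.** The plan states no figure to reproduce here. The check is on the definitions, followed by an illustration of scale.

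**Step 1. Follow one subject through the text.** The subject consents, is eligible and is randomised (Protocol 8.5.2). Surgery starts, an adverse event occurs, and implantation is abandoned (7.8.1). The subject becomes a Screen Failure and is not counted (7.6, 7.8.1, 9.1.3), while enrolment continues to 170. The subject is not in SAF (Protocol 10.2, SAP 7.2) and so not in the safety summaries (Protocol 10.5, SAP 7.13). The SAP's full analysis set requires implantation, and the per-protocol set is a subset of it. Neither the disposition summary (SAP 7.6) nor any other section asks for randomised-not-implanted subjects by arm, or says how their events are reported.

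**Step 2. Compare the outcomes of an operation.**

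| What the hip receives | Screen Failure under 7.6 | Screen Failure under 7.8.1 and 9.1.3 | SAF under SAP 7.2 |
|---|---|---|---|
| Assigned system | No | No | Yes, as assigned |
| Neither system | Yes | Yes | No |
| Control, though assigned OR3O | No, a system was implanted | Depends on what study device means | Yes, under control |
| OR3O, though assigned control | No, a system was implanted | Depends on what study device means | Yes, under OR3O |

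The second row is the loss. The third row is misattribution: an event during an attempted OR3O implantation is tabulated under control. In the last two rows the Screen Failure definitions can disagree, because 7.6 refers to either system while 7.8.1 and 9.1.3 refer to the study device.

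**Step 3. Check the AE window against enrolment.** The window opens at enrolment (8.4.4), and enrolment requires implantation (7.6). An event earlier in the same operation precedes the window, yet the same sentence says intra-operative events are included. The two statements cannot both hold.

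**Step 4. Scale.** Let q be the share of randomised subjects who receive neither system. The documents do not give q, so it is assumed. With enrolment continuing to 170 implanted:

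- expected number outside SAF = 170/(1 − q) − 170
- chance of at least one such subject among the first 170 randomised = 1 − (1 − q)^170

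| Assumed q | Expected outside SAF | Chance of at least one |
|---|---|---|
| 0.5% | 170/0.995 − 170 = 0.9 | 57% |
| 1% | 170/0.99 − 170 = 1.7 | 82% |
| 2% | 170/0.98 − 170 = 3.5 | 97% |
| 5% | 170/0.95 − 170 = 8.9 | over 99.9% |

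These counts cover both arms and every reason for non-implantation, including withdrawal shortly before surgery. Operated subjects with an intra-operative event are a subset.

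**The case against.** The strongest reply is that these events are recorded. Protocol 8.4.4 and SAP 5.7 name intra-operative AEs. Protocol 9.1.3 lists AEs and device deficiencies among the intra-operative data and has data transcribed to the eCRF. Protocol 12.3 requires AEs of any kind and device deficiencies to be recorded. A reader might infer from the enrolment definition that AE collection begins only at successful implantation, and the documents do not support that. The fault is a contradictory window, plus loss at the analysis stage. Recording an event does not bring it into a summary restricted to SAF.

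A reader might also infer that every event preventing the assigned implant is lost. That goes too far. Protocol 6.5 provides for device replacement during the primary surgery, and SAP 7.2 keeps a hip that received the other system. Loss needs neither system to be implanted.

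Two partial safeguards exist. Device deficiencies occurring on study are to be listed (SAP 7.13), but on study is not defined and the same section puts safety endpoints on SAF. The Screening and Enrollment Log (Protocol 7.4) records reasons for exclusion, but nothing requires tabulation by arm.

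Finally, it is tempting to assume a few abandoned implantations per arm and set the rate beside the 0.9% dislocation rate in Protocol 4.2. The documents support neither the count nor the comparison: they give no non-implantation rate, and dislocation is a different event. Because Screen Failures are not counted, enrolment also continues past them, so the reported denominator does not shrink below 85 per arm under the plan.

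**Conclusion.** The point holds in this form: followed as written, the plan leaves operated subjects who receive neither system out of all SAF-based safety summaries, and no other provision clearly brings them back. Two text conflicts go with it, one between the AE window and the enrolment definition, the other between the Screen Failure wordings. A hip that crosses to the other system is kept, but its event can be attributed to the wrong construct.

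The size cannot be established from the documents. The figure of about 1 to 9 subjects rests on an assumed 0.5% to 5% non-implantation rate and on the planned 170 implanted. The SAP says the study was terminated early, so the actual number may be smaller, and it may be zero. The correction is worth making because the exclusion follows randomisation, may depend on the device, and affects an objective the trial calls primary.

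**What to change.** Use the addendum or amendment route in SAP section 2, before reporting:

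- Define the safety set as all randomised subjects in whom surgery was started.
- Tabulate or list AEs and device deficiencies by assigned device and by device attempted or received, so that an event during an attempted OR3O implantation is visible as such.
- Report randomised-not-implanted subjects by arm, with the reason and whether surgery had begun.
- State the AE window so that it opens no later than the start of surgery, and reconcile Protocol 7.6 with 8.4.4.
- Reconcile the Screen Failure wording in Protocol 7.6, 7.8.1 and 9.1.3, including the status of a hip that receives the other system.

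The cost is SAP and protocol wording and a few extra subjects in the tables. Because the study has stopped, the fix reaches only what was actually recorded. The documents do not confirm that operative eCRF pages were completed for Screen Failures. The sponsor should check this, and the report should say where data are missing.
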